10.3.2 Analysis Plans for Secondary Objectives

Confidence intervals for the clinical benefit rate will be calculated similarly to RR. Progression-free survival times will be estimated using the Kaplan-Meier method. The objective response rate by irRC will be estimated similarly. Confidence intervals on the median will be constructed. Toxicities will be tabulated.

10.3.3 Analysis Plans for Exploratory Objectives

All biological parameters other than PD-L1 ligand expression will be measured pre and post treatment (either in plasma or tumor) or Day 1 and Day 5 (LINE1 methylation in PBMCs). Pre-treatments vs post-treatment or Day 1 to Day 5 comparisons will be made by paired t-tests (or Wilcoxon Signed-Rank tests if the data are not normally distributed). PD-L1 ligand expression from archival tissue will be summarized descriptively. Pre-treatment (including PD-L1 ligand expression) and pre-post changes in parameters will be correlated with response by Fisher-Exact test for RR, CBR, and log rank test for PFS (using the maximal chi-square cut-point for the parameter).

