1.5 Exploratory Studies

To test the hypothesis that the combination of guadecitabine and pembrolizumab reactivates immune responses by allowing re-expression of tumor antigens silenced epigenetically, we will measure several exploratory endpoints. All biological parameters will be correlated with clinical endpoints (ORR, CBR, and PFS).

- NY-ESO-1 and *MAGE* antigens' promoter methylation (pyrosequencing) and mRNA expression levels (quantitative RT-PCR) will be measured before and after treatment in DNA (plasma and tumor biopsies) and RNA (tumor biopsies), respectively.
- Cytokine response (IFN γ , IL2, IL6, IL10, TNF α) will be measured in plasma by ELISA.
- Expression of the PD-L1 ligand will be measured by IHC in archival tumors.
- Measure LINE 1 methylation in DNA extracted from PBMCs (D5 vs. D1 of cycles 1 and 2).
- Tumor infiltrating lymphocytes (TILs) will be quantified in tumor biopsies before and after treatment (IHC), including in optional samples collected > 6 months on treatment.

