2.3 Exploratory Objectives & Endpoints

- NY-ESO-1 and MAGE antigens' promoter methylation (pyrosequencing) and mRNA expression levels (quantitative RT-PCR) will be measured before and after treatment in DNA (plasma and/or tumor biopsies) and RNA (tumor biopsies), respectively.
- Cytokine response (IFN γ IL2, IL6, IL10, TNF α) will be measured in plasma by ELISA.
- Measure LINE 1 methylation in DNA extracted from PBMCs (measured on days 1 and 5 of cycles 1 and 2).
- Expression of the PD-L1 ligand will be measured by IHC in archival tumors.
- Tumor infiltrating lymphocytes (TILs) will be quantified in tumor biopsies before and after treatment (IHC), including in optional samples collected > 6 months on treatment.

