10.2 Sample Size and Accrual

We will utilize the optimum two-stage design and we anticipate enrolling 35 evaluable patients. This two-stage design to test the null hypothesis that $RR \leq 0.10$ versus the alternative that $RR \geq 0.30$ (where RR is calculated via RECIST v1.1) has an expected sample size of 22.5 and a probability of early termination of 0.71 when $RR = 0.10$. If the drug combination is actually not effective, there is a 0.047 probability of concluding that it is (the target for this value was 0.050). If the drug is actually effective, there is a 0.098 probability of concluding that it is not (the target for this value was 0.100). Subjects who are not evaluable for response will be replaced so up to 46 subjects may be enrolled.

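### Section 10.3.3 relates quantitative markers to response only after an unspecified cut: a searched cut inflates false positives, a fixed cut usually loses power, and a rank test avoids both.

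*Combined protocol and SAP*

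**What the plan says.** Section 1.5 sets the aim: "All biological parameters will be correlated with clinical endpoints (ORR, CBR, and PFS"). Section 10.3.3 gives the method. For pre-treatment values and changes, "pre-post changes in parameters will be correlated with response by Fisher-Exact test for RR, CBR", followed by the "log rank test for PFS (using the maximal chi-square cut-point for the parameter").

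The markers are mostly measurements on a scale. Section 2.3 lists "promoter methylation (pyrosequencing) and mRNA expression levels (quantitative RT-PCR) will be measured before and after treatment", cytokines that "will be measured in plasma by ELISA", LINE-1 methylation in PBMCs, and quantified tumor-infiltrating lymphocytes. PD-L1 is measured by IHC, with no scoring rule given.

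For the paired pre/post comparison, the same section keeps the measurements whole, using "paired t-tests (or Wilcoxon Signed-Rank tests if the data are not normally distributed"). It plans no rank-sum test, logistic model or other uncut analysis of marker against response or clinical benefit.

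On size, section 10.2 says "we anticipate enrolling 35 evaluable patients", with response rates of 0.10 (null) and 0.30 (alternative). No power, level or decision rule is stated for the marker analyses.

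**The concern.** Fisher's exact test works on categories, so every quantitative marker must be cut before it can be related to RR or CBR. The plan leaves open how.

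The parenthesis naming the maximal chi-square cut-point follows the PFS clause. Read one way, it also governs the Fisher tests. The cut is then chosen because it separates responders best, and the ordinary p-value ignores that search. Read the other way, the Fisher tests have no stated cut, and whatever fixed cut is chosen discards the ordering of the values within each half.

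At stake is the trial's mechanistic question: whether marker levels or changes go with response. Patients have paired biopsies and repeated blood draws for it. With few responders, one reading would report too many associations and the other would usually find too few.

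**Working it through.** **Inputs from the documents.** N = 35 evaluable and response rates 0.10 and 0.30 (section 10.2); Fisher's test and the cut-point wording (section 10.3.3); stage 1 of 18 patients with bound 2, and final bound 6 of 35 (section 10.4.2).

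**Assumptions not in the documents.** A normally distributed marker with responders shifted by 1 SD; two-sided 0.05; a median cut (17 high, 18 low) as the fixed cut; the maximal cut searched over the inner 10–90% of values; 25 patients as a smaller tissue set.

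**1. The plan's own figures.** An exact binomial calculation, counting objective responses at both stages, gives type I error 0.0474, type II error 0.0984 and expected N 22.53, matching the stated 0.047, 0.098 and 22.5. Early termination at 0.10 comes out at 0.734, not the stated 0.71. The stated expected N agrees with 0.734: 18 + 17 × (1 − 0.734) = 22.5, while 0.71 would give 22.9. This does not affect the present point. Expected responders are 35 × 0.10 = 3.5 to 35 × 0.30 = 10.5.

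**2. What Fisher's test can do at a median cut.**
- 3 responders: the most extreme table has probability C(17,3)/C(35,3) = 680/6545 = 0.104. The test can never reach 0.05.
- 4 responders: all high has probability 2380/52360 = 0.045, which is significant. All low has at least 3060/52360 = 0.058, which is not.
- 7 responders: 6 of 7 high gives 0.0331 + 0.0029 + 0.0047 = 0.041, which is significant. 6 of 7 low gives 0.0469 + 0.0047 + 0.0029 + 0.0331 = 0.088, which is not.

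So the result depends on the direction of the effect and on which half takes the odd patient.

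**3. Simulation at N = 35** (20,000 runs per alternative, 40,000 under the null; rank-sum p-values exact). The shift is 1 SD upward.

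| Responders | Rank-sum power | Fisher, median cut: power | Fisher, maximal cut, unadjusted: false-positive rate | Same: rejection rate at 1 SD | Maximal cut held at 5%: power |
|---|---|---|---|---|---|
| 5 | 0.48 | 0.31 | 0.17 | 0.66 | 0.40–0.41 |
| 7 | 0.60 | 0.52 | 0.21 | 0.79 | 0.45–0.49 |
| 10 | 0.71 | 0.55 | 0.21 | 0.85 | 0.61–0.62 |
| 11 | 0.72 | 0.42 | 0.21 | 0.87 | 0.63 |
| 17 (CBR-like) | 0.80 | 0.55 | 0.28 | 0.93 | 0.70 |

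The last column gives the two ways of recalibrating, on the chi-square statistic or on the Fisher p-value. With 3 responders, power is 0.32 for rank-sum, 0.00 for the median cut and 0.16–0.24 for the recalibrated maximal cut. Across 3 to 11 responders the unadjusted false-positive rate is 0.14 to 0.21.

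If the shift is downward, rank-sum power is essentially unchanged, but median-cut Fisher has 0.35 with 5 responders, 0.20 with 7 and 0.28 with 10.

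**4. Gaps from the rounded figures.** Rank-sum minus median-cut Fisher, upward shift, 5 to 11 responders: 0.60 − 0.52 = 0.08 up to 0.72 − 0.42 = 0.30. Rank-sum minus the maximal cut held at 5%: 0.48 − 0.41 = 0.07 up to 0.32 − 0.16 = 0.16.

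**5. Smaller set (assumed).** With 25 patients and 5 responders: 0.43 for rank-sum, 0.26 at the median cut and 0.36–0.38 at the recalibrated maximal cut.

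**The case against.** A reader might infer that the planned test is simply conservative and will miss associations. The documents do not support that as stated. The only cut rule they contain is the maximal chi-square one, and with an unadjusted p-value it rejects more often than the rank test (0.79 against 0.60 with 7 responders). The harm on that reading is false positives; the power deficit appears only once size is held at 5%. The median cut is not in the documents, so its losses apply only if some such fixed cut is what is meant.

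A reader might also infer that a rank test is always better. It is not. The hypothesis concerns re-expression of silenced antigens, which could behave more like off/on than a shift. When responders fall above the median with probability 0.9 (a step at the cut), Fisher leads with 4 responders (0.40 against 0.21) and 7 (0.46 against 0.36), though not with 10 (0.42 against 0.46). Even for a shift, the two tests tie at 4 responders if it is upward (0.41 each). Fisher's test also extends beyond 2×2 tables, so a marker scored in several categories need not be split in two. Nothing in the documents says that PD-L1 is scored positive/negative.

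The phrase very few responders fits RR. CBR adds stable disease of at least 3 months, so its count will probably be larger and is not given; the 17-of-35 row is only illustrative.

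Finally, these are exploratory analyses with no stated level, power target or decision rule. That stands and lowers the severity. It does not supply the missing cut rule or an uncut analysis.

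**Conclusion.** The concern holds in a conditional form. Section 10.3.3 forces quantitative markers into categories to relate them to RR and CBR, and leaves the rule for doing so unclear. Both readings do worse than a rank-sum test for a marker whose distribution shifts with response: one through a per-test false-positive rate three to four times 5% at RR-size groups (higher at CBR-like sizes), the other usually through lost power. The fixed-cut loss is not a stable number, because it changes with the responder count and the direction of the effect. All power figures rest on the assumed 1 SD normal shift and 0.05 level, and the ordering can reverse for a true step relation. Severity is low, since no trial decision uses these results; what suffers is the reliability of the mechanistic findings.

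**What to change.** In section 10.3.3, compare continuous markers and their pre-post changes between responders and non-responders, and between patients with and without clinical benefit, by the exact Wilcoxon rank-sum test, reporting the AUC with a 95% interval. Keep Fisher's exact test only for markers scored as categories, and include PD-L1 there only if the plan states that it is scored that way. Make any cut-point analysis, for response or for PFS, secondary, state how the cut is chosen, and report a permutation-adjusted p-value that repeats the cut search.

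The cost is a few sentences of wording and a short permutation routine, with no new data, samples or visits. The price is some loss of power for a marker with a true on/off relation to response; the secondary cut-point analysis partly covers that case.

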4. Tumor response assessment will consist of evaluation by CXR or CT scans of chest and MRI or CT of abdomen and pelvis. Screening radiologic imaging should be done ≤ 28 days prior to registration. During treatment, radiologic imaging should be done prior to Cycle 3 and cycle 5 and then prior to every third cycle thereafter (e.g. prior to cycles 8, 11, 14, etc.). *Radiologic imaging can be obtained ≤ 7 days prior to day 1 of the cycle.* The imaging modality selected for each subject should remain the same throughout the study. *Responses of PD, PR, or CR should be confirmed within 4-6 weeks, at the discretion of the treating physician.* (Refer to section 6.0 for more details).
5. Formalin fixed paraffin-embedded tissue will be requested from an archived tumor specimen from all subjects (required to submit, if available). The archived tumor tissue specimens may be from surgery or from a diagnostic biopsy of primary or metastatic tumor specimen, and may be procured up to 3 months from registration. Unavailability of archived tissue will not render subject ineligible for study. See Section 9 and laboratory manual for additional details.
6. Blood for DNA analysis will be collected on Cycle 1 Day 1 [≤ 7 days] and Cycle 2 Day 8 [+2 days]. See Section 9 and laboratory manual for additional details.
7. Blood for cytokine response will be collected at pre-treatment on Cycle 1 Day 1 (≤ 4 days), Cycle 2 Day 1 (≤ 4 days), Cycle 3 Day 1 (≤ 4 days), and at the safety follow up visit. See Section 9 and laboratory manual for additional details.
8. Pregnancy test required only for females of child-bearing potential ≤ 7 days prior to registration. Also, pregnancy test will be done on D1 (≤ 4 days) of each cycle for females of child bearing potential.
9. Blood for PBMC analysis will be collected at pre-treatment Cycle 1 Day 1 (≤ 4 days), Cycle 1 Day 5, pre-treatment on Cycle 2 Day 1 (≤ 4 days), Cycle 2 Day 5, and at the safety follow up visit. See Section 9 and laboratory manual for additional details.
10. Tumor biopsies [guided by CT, ultrasound, or physical exam, according to the discretion of the treating physician], and/or paracentesis, and/or thoracentesis will occur after registration and prior to the start of treatment [(Cycle 1 Day 1 (≤ 7 days)) and Cycle 2 Day 8 (+2 days) if clinically feasible for the subject. See Section 9 and laboratory manual for additional details.

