6.3 Secondary Endpoints

Measure progression free survival (PFS) and clinical benefit rate (CBR) to the combination of guadecitabine and pembrolizumab.

PFS will be defined as the time from first dose of study treatment until disease progression or death from any cause. Any patient who has completed at **least 1 cycle of treatment** will be evaluable for PFS endpoint.

Clinical Benefit Rate(CBR) will be defined as patients with CR + PR or SD (SD for at least 3 months). Any patient who has completed at **least 2 cycles of treatment** will be evaluable for CBR endpoint.

Measure toxicity profiles for the combination of guadecitabine and pembrolizumab. The number, type, grade, severity, and frequency of adverse events will be tabulated; adverse events are assessed at least once per cycle. Any patient who receives **at least one dose** of study therapy will be evaluable for toxicity endpoints.

Measure objective response rate (ORR) to the combination of guadecitabine and pembrolizumab using the Immune Related Response Criteria (irRC)
(Note: Response assessments will be made both using the irRC, and using RECIST v1.1, allowing additional comparisons among these criteria for disease response assessment. Measurable and non-measurable lesions will be followed by both RECIST v1.1 & irRC. Disease progression will be determined using RECIST 1.1 criteria).

6.4 Exploratory Objectives:

To test the hypothesis that the combination of guadecitabine and pembrolizumab reactivates immune responses by allowing re-expression of tumor antigens silenced epigenetically, we will measure several endpoints:

- NY-ESO-1 and MAGE antigens' promoter methylation (pyrosequencing) and mRNA expression levels (quantitative RT-PCR) will be measured before and after treatment in *DNA (plasma and/or tumor biopsies)* and *RNA (tumor biopsies)*, respectively.
- Cytokine response (IFN γ , IL2, IL6, IL10, TNF α) will be measured in plasma by ELISA.
- Measure LINE 1 methylation in DNA extracted from PBMCs (D5 vs. D1 of cycles

NU Study Number: NU 16G03
Merck Study Number: 3475-244

1 and 2).

- Expression of the PD-L1 ligand will be measured by IHC in archival tumors.
- Tumor infiltrating lymphocytes (TILs) will be quantified in tumor biopsies before and after treatment (IHC).

All biological parameters will be correlated with clinical endpoints (ORR and PFS).

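### Biomarker–PFS log-rank tests at the maximal chi-square cut-point carry no corrected p-value or search limit; read at a nominal 0.05, each continuous marker has roughly a 30–60% false-positive rate

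*Combined protocol and SAP*

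**What the plan says.** Section 10.3.3 covers baseline values (including PD-L1) and changes on treatment. For response it plans the following: "Pre-treatment (including PD-L1 ligand expression) and pre-post changes in parameters will be correlated with response by Fisher-Exact test for RR, CBR". For PFS it plans a "log rank test for PFS (using the maximal chi-square cut-point for the parameter".

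The scope is wide. Section 1.5 says "All biological parameters will be correlated with clinical endpoints (ORR, CBR, and PFS"; Section 6.4 repeats this for response and PFS.

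Neither Section 10.3.3 nor any other section names a corrected or permutation p-value, limits on where the cut may fall, a validation step, a significance level for these tests, or a multiplicity adjustment. The only adjustment in Section 10.3 is for the confidence interval after the two-stage design (10.3.1), which is named and given a reference. The reference list has nothing on maximally selected statistics.

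**The concern.** A log-rank statistic is referred to the 1-df chi-square because the groups are fixed without looking at the outcome. Here the outcome chooses the groups. The reported statistic is the maximum over up to n − 1 correlated tests, so a p-value taken from the 1-df distribution is too small. The separation of the curves at the chosen cut is exaggerated for the same reason.

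The exploratory label excuses limited multiplicity control across markers. It does not make an individual p-value valid. These analyses serve the trial's stated mechanistic hypothesis, and the blood and tissue samples are listed as mandatory in Section 9.0, apart from the optional sample at 6 months or later. At stake are the biomarker conclusions and any later study that reuses the cut-points. The paired pre/post tests and the primary response analysis are not touched.

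**Working it through.** **The plan's own figures.** The plan states no error rate for the biomarker tests. The error rates it does state belong to the two-stage response design (18 then 35 patients, boundaries 2 and 6, rates 0.10 and 0.30). Counting objective responses at both stages, exact binomial calculation gives type I error 0.0474 and type II error 1 − 0.9016 = 0.098, matching the stated 0.047 and 0.098. Neither figure protects the biomarker tests.

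**Inputs from the documents**
- Sample size: 35 evaluable for response. Section 10.2 adds "Subjects who are not evaluable for response will be replaced so up to 46 subjects may be enrolled", and PFS needs only one completed cycle (6.3), so 42 and 46 were also run.
- Scan times (Section 5.1, footnote 4): "During treatment, radiologic imaging should be done prior to Cycle 3 and cycle 5 and then prior to every third cycle thereafter". With 21-day cycles, the scan before cycle c falls at week 3(c − 1). Cycles 3, 5, 8 and 11 give weeks 6, 12, 21 and 30.

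**Assumptions not in the documents**
- A result is called positive if chi-square exceeds 3.84.
- The marker is continuous and independent of PFS.
- PFS is exponential with median 13 weeks (range 6 to 22) and censoring is 5–30%.

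**Statistic.** For cut c, X²(c) = [Σ(d₁ − d·n₁/n)]² / ΣV, summed over event times. The plan's rule reports max X²(c) over all c.

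**One-patient illustration.** Take n = 35 and no ties or censoring before the first event. If the patient with the lowest or highest marker value progresses first, cutting off that one patient gives O − E = 1 − 1/35 = 34/35 and V = (1/35)(34/35). Then X² = (34/35)² / (34/35²) = 34. This happens by chance with probability 2/35 = 0.057. An unlimited search can therefore show an enormous statistic that rests on one patient.

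**False-positive rate, n = 35 (3,000–4,000 null data sets per setting)**

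| Search range | Progression on planned scans | Across median PFS 6–22 weeks (on scans) | Untied times |
|---|---|---|---|
| Any cut (as written) | 0.55 | 0.44–0.59 | 0.60–0.63 |
| Central 80% | 0.39 | 0.36–0.40 | 0.42–0.43 |
| Central 60% | 0.30 | 0.28–0.30 | 0.31–0.33 |

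A pre-specified median split gives 0.05–0.06. At n = 46 the three search ranges give 0.56–0.66, 0.41–0.44 and 0.30–0.31. Narrower searches give 0.23–0.27 (central half) and 0.17–0.20 (central third).

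**Cross-checks.** A separate simulation with untied times and 0–40% censoring gave 0.60–0.65 (any cut), 0.40–0.42 (central 80%) and 0.31–0.32 (central 60%) at n = 35. The Miller–Siegmund approximation, with b = 1.96 and a fraction e trimmed at each end, is P ≈ 4φ(b)/b + φ(b)(b − 1/b)·ln[(1 − e)²/e²]. For e = 0.20: 0.119 + 0.0847 × 2.773 = 0.354. For e = 0.10: 0.119 + 0.0847 × 4.394 = 0.492. These large-sample values lie somewhat above the simulated ones.

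**Apparent effect.** With a true hazard ratio of 1, the median apparent hazard ratio exp(|O − E|/V) at the selected cut (central 60%) is 2.1–2.3, against 1.3–1.4 at a median split.

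**Across markers.** Section 2.3 lists at least 12 parameters by my count: methylation and mRNA for NY-ESO-1 and MAGE (4), five cytokines, LINE-1, PD-L1 and TILs. All but PD-L1 have baseline and change values: 11 × 2 = 22 PFS tests. If all are continuous, chance positives are 22 × 0.30 = 6.6 with a central-60% search and 22 × 0.55 = 12.1 with any cut. A valid 5% test gives 22 × 0.05 = 1.1.

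**The case against.** - **No level is set.** The plan sets no significance level and no decision rule, and calls the work exploratory. This stands as a condition: the false-positive rate exists only once a nominal 0.05 and the 1-df reference are applied. An uncorrected p-value from this procedure is still misleading at any threshold.
- **The range mixes two procedures.** The lower end of 30–60% needs a trimmed search that the plan does not contain. That is correct. As written, the upper end applies, so the lower figure is generous to the plan.
- **Not every marker is continuous.** Coarse scores with three to five levels, possible for IHC, give 0.10–0.20. If half the values of a marker are undetectable, the rates are about 0.33, 0.23 and 0.21 (any cut, central 80%, central 60%); at 70% undetectable, 0.26, 0.17 and 0.14. The count of about 7 therefore falls if many markers are like this. All these rates remain at least twice nominal.
- **Tissue samples may be few.** Biopsies are taken only if feasible. With 15–20 patients and progression on scans, the any-cut rate is about 0.39–0.48. The defect is smaller there but does not disappear.
- **The wording could mean something else.** It might intend one cut per marker chosen on response (under illustrative assumptions, a PFS rate of about 0.08–0.10), or a maximally selected test with its own null distribution. Neither is stated or referenced, and the phrase is attached to the log-rank test for PFS.
- **A continuous main analysis goes beyond the defect.** This is fair: a corrected p-value with a stated range would suffice.

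**Conclusion.** The concern holds. The stated rule selects the cut by the outcome and then tests at that cut, with no correction anywhere in the documents. For a continuous marker read at nominal 0.05, the false-positive rate at n = 35 is about 0.30 with a central-60% search and about 0.55–0.63 with the unlimited search the text allows. It is lower, about 0.10–0.33, for coarse markers or those with many undetectable values. Median PFS and censoring are assumed, but the result moves little over the ranges tried.

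The matter should be corrected before the biomarker analysis. It affects no trial decision and not the primary endpoint. Whether the cut-point rule also governs the Fisher tests is unclear. If it does, the any-cut rates at n = 35 would be about 0.15, 0.23 and 0.28 for outcome proportions of 0.1, 0.3 and 0.5.

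**What to change.** Amend Section 10.3.3 as follows.

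1. If a maximal chi-square cut-point is shown, state the search range in advance (for example the 20th to 80th percentile). Report a permutation or maximally-selected-statistic p-value and label the cut-point and its hazard ratio as unvalidated. This is the essential change.
2. State whether the cut-point rule applies to the Fisher tests for response and clinical benefit; if so, apply the same correction.
3. Preferably, make the main analysis continuous or rank-based: a Cox model for PFS, and Wilcoxon rank-sum or exact logistic regression for response and clinical benefit.

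In simulation, the permutation p-value over the 20th–80th percentile range (199 permutations, progression on scans, n = 35) had a false-positive rate of 0.054, and a rank-based Cox score test 0.06. A corrected critical value gave 4.8–5.2%. At n = 35 it requires a chi-square of about 8.7 (central 60%) or 10.5 (central 80%) in place of 3.84.

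The cost is one paragraph and a few lines of code, with no new data. The downside is fewer nominally significant exploratory results.
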